#### **9.2.5. Follow-Up Period**

##### **9.2.5.1. SCRI**

In the SCRI analysis, follow-up for the risk period will begin upon (for the outcomes of anaphylaxis and convulsions/seizures) or one day after (for all other outcomes) receipt of the COMIRNATY 2023-2024 Formula ([Table 2](#)) and continue until the earliest of:

- Receipt of a COVID-19 vaccine other than the COMIRNATY 2023-2024 Formula;
- The end of the outcome-specific risk interval as defined in [Section 9.3.2](#);
- Disenrollment from the health plan, death, or the end of data collection.

After the outcome-specific pre-specified washout period following the risk interval, follow-up for the control period will begin and continue until the earliest of:

- Receipt of a COVID-19 vaccine other than the COMIRNATY 2023-2024 Formula;
- The end of the control period as defined in [Section 9.3.2](#);
- Disenrollment from the health plan, death, or the end of data collection.

Individuals will be followed for each safety outcome during both the risk and control periods, such that events observed during the risk period or washout period will not censor follow-up for the control period.

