### 9.2.5.2. Cohort Study

In the cohort study (Phase 2), depending on the safety outcome of interest, follow-up will begin on cohort entry or the day following cohort entry ([Table 2](#)) and extend until the earliest of:

- The occurrence of an outcome of interest ([Section 9.3.2](#));
- For COMIRNATY 2023-2024 Formula recipients, receipt of a COVID-19 vaccine other than the COMIRNATY 2023-2024 Formula; for comparators whose qualifying healthcare encounter is for a non-COMIRNATY 2023-2024 Formula COVID-19 vaccination, receipt of a different brand of COVID-19 vaccine from cohort entry;
- One year after cohort entry;
- Disenrollment from the health plan, death, or the end of data collection;

Those comparators who later receive a dose of COMIRNATY 2023-2024 Formula may be eligible for inclusion in the COMIRNATY 2023-2024 Formula cohort if they meet the eligibility criteria for cohort entry.

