### 9.3.1.2. Comparator Cohort

The Phase 2 cohort study will include comparators with no recorded vaccination for the COMIRNATY 2023-2024 Formula. To improve comparability with the COMIRNATY 2023-2024 Formula vaccinated cohort, patients included in the comparator cohort will be required to have a code indicative of a healthcare encounter, including one of the following:

- Presence of a code for a vaccine other than the COMIRNATY 2023-2024 Formula;
- Presence of a code indicative of an outpatient healthcare encounter.

Codes relating to other vaccines or outpatient visits are provided in [Annex 2 \(Appendix II\)](#).

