#### **9.7.2.2. Primary Analysis**

Once the matched cohorts have been created, the incidence rate of each safety outcome will be estimated among the COMIRNATY 2023-2024 Formula-exposed group and its matched comparator group. The rate ratio will be estimated using unconditional Poisson regression that accounts for both the matching ratio (i.e., a weight representing the number of COMIRNATY 2023-2024 recipients divided by the number of comparators in each individual strata) and individuals who are included in both study cohorts (i.e., using a REPEATED statement with an independent working correlation structure). If standardized differences show covariate imbalances in the matched cohorts, imbalanced covariates will be included in the unconditional Poisson models.

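### Comparators who entered the cohort on a non-COVID-19 vaccine or an outpatient visit are not censored at a later COMIRNATY 2023-2024 dose, so recorded exposed time counts as unexposed

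*Protocol*

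**What the plan says.** Protocol section 9.3.1.2 admits comparators by two routes: "Presence of a code for a vaccine other than the COMIRNATY 2023-2024 Formula", which covers other-brand COVID-19 vaccines and non-COVID-19 vaccines alike, and "Presence of a code indicative of an outpatient healthcare encounter".

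Section 9.2.5.2 lists the ends of follow-up. Besides the outcome and one year, there is a general end: "Disenrollment from the health plan, death, or the end of data collection". Only two groups have a vaccine-based end:

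- the exposed arm: "For COMIRNATY 2023-2024 Formula recipients, receipt of a COVID-19 vaccine other than the COMIRNATY 2023-2024 Formula";
- one part of the comparator arm: "for comparators whose qualifying healthcare encounter is for a non-COMIRNATY 2023-2024 Formula COVID-19 vaccination, receipt of a different brand of COVID-19 vaccine from cohort entry".

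The section then provides for crossover: "Those comparators who later receive a dose of COMIRNATY 2023-2024 Formula may be eligible for inclusion in the COMIRNATY 2023-2024 Formula cohort", subject to the eligibility criteria. It does not say what happens to comparator follow-up at that dose.

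Section 9.7.2.2 addresses the overlap in the model. The unconditional Poisson regression accounts for "individuals who are included in both study cohorts (i.e., using a REPEATED statement with an independent working correlation structure").

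Sections 8.2 and 9.3.1.2 define the contrast as COMIRNATY recipients against people with no recorded dose of it, over up to one year.

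**The concern.** For a comparator who entered on a flu shot or an office visit, a later COMIRNATY dose matches none of the listed ends of follow-up. A programmer who follows the list keeps that person in the comparator arm through the dose. If the person also qualifies for the COMIRNATY cohort, the same days and the same event can be counted in both arms. If the person does not qualify, for example because the dose falls after accrual closes on 31 March 2024, the exposed time counts as unexposed only.

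Either way, the comparator rate contains vaccine-exposed experience, and any true excess shrinks. This affects the Phase 2 primary estimate, in a post-authorization safety study that is a condition of authorization. Section 9.9 also makes the cohort the primary analysis for chronic outcomes such as multiple sclerosis. Two of the three comparator subsets in section 9.7.2.3 (non-COVID-19 vaccine, other outpatient encounter) inherit the problem and the other-brand subset does not, so the three secondary comparisons run under different censoring rules.

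**Working it through.** The protocol states no crossover rate, event rate or power, so there is no figure of its own to reproduce. The check has two parts.

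**Who is censored at a later COMIRNATY dose, by entry route (9.3.1.2 against 9.2.5.2)**

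- Other-brand COVID-19 vaccine: yes, because COMIRNATY is a different brand.
- Non-COVID-19 vaccine: no rule.
- Outpatient visit: no rule.

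The crossovers that 9.2.5.2 foresees come from the two routes without a rule. Accrual runs from 11 September 2023 to 31 March 2024, which is 203 days. An other-brand comparator who gets COMIRNATY within that span is at most 202 days from the first vaccine, and 9.2.2.2 excludes anyone with a COVID-19 vaccine in the previous 270 days.

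The REPEATED statement with an independent working correlation changes the standard error. It does not move person-time or events from one arm to the other.

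**Size, case A: effect lasting through follow-up**

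Let c be the share of comparator person-time after COMIRNATY (assumed), R the true RR and λ the unexposed rate. The exposed rate is λR and the comparator rate is λ[(1 − c) + cR], so

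observed RR = R / [1 + (R − 1)c].

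- R = 3: 3/1.10 = 2.73 at c = 5%; 3/1.20 = 2.50 at 10%; 3/1.40 = 2.14 at 20%.
- R = 2: 2/1.05 = 1.90; 2/1.10 = 1.82; 2/1.20 = 1.67.
- R = 0.7 at c = 10%: 0.7/0.97 = 0.72, so the pull is toward 1 from below as well.
- Section 9.3.2 sets the signal threshold at an RR above 3.0 with P below 0.01. A true RR of 3.5 reads 3.0 when c = (3.5/3 − 1)/2.5 = 6.7%.

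The other-brand comparators lower c. Suppose a share s of comparators is other-brand, and 20% of the rest cross over at day 60 on average (both assumed). Then c = (1 − s) × 0.20 × 305/365:

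- s = 0: c = 16.7%, and R = 3 reads 2.25.
- s = 30%: c = 11.7%, and R = 3 reads 2.43.
- s = 50%: c = 8.4%, and R = 3 reads 2.57.

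**Size, case B: effect confined to a 42-day window**

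Table 2 has no risk interval longer than 42 days. Let p be the share of comparators who cross over (assumed), with the whole window inside 365 days of follow-up:

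observed one-year RR = [1 + (42/365)(R − 1)] / [1 + p(42/365)(R − 1)].

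For R = 3, (42/365) × 2 = 0.230.

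- p = 0: 1.230, which is 1.23.
- p = 5%: 1.230/1.0115 = 1.22.
- p = 10%: 1.230/1.0230 = 1.20.
- p = 20%: 1.230/1.0460 = 1.18.

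The share of the excess lost is about 6%, 12% and 24%.

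**After the fix:** c = p = 0. Case A returns R and case B returns 1.23, if censoring is non-informative.

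**The case against.** The best defence is that censoring is implied: comparators are defined by having no recorded dose, so their comparator status should lapse at the dose. The definition does point that way, and nothing in the protocol says in terms that follow-up continues. But 9.2.5.2 is the operative list. It spells out the brand-switch rule for other groups and omits this event for these comparators. The definition cannot mean that anyone dosed later is removed altogether, because 9.2.5.2 and 9.7.2.2 both provide for people in both cohorts. So double counting is permitted by the text rather than stated as the intention. The REPEATED statement is not evidence of it, since that statement would be needed even if crossovers were censored.

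It can also be said that section 9.9 already concedes exposure misclassification biased toward the null. That passage concerns doses that never reach the claims data. Here the dose is recorded and the error is avoidable.

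The limit on severity stands. Section 9.3.2 makes record review mandatory only for a signal in the primary analysis of the self-controlled risk interval (SCRI) design. In other analyses it is optional, so this dilution does not touch the mandatory trigger.

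A reader might infer that the SCRI has the same fault, because its windows end at "Receipt of a COVID-19 vaccine other than the COMIRNATY 2023-2024 Formula" and not at a further COMIRNATY dose. The protocol does not support that. The SCRI has no unexposed arm to contaminate. Section 9.1.1 names a small group who may have repeat doses and provides for a first-dose analysis and a pooled repeat, and section 9.2.3 makes each dose a new vaccination date in the multi-dose analysis.

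A reader might also want every comparator censored at any COVID-19 vaccine, for symmetry. Other-brand recipients are legitimate comparators under 9.3.1.2 and 9.7.2.3, so a later other-brand dose is not misclassification in the primary contrast. Such a rule would also break the existing different-brand rule. It is a design preference and no correction of an error.

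**Conclusion.** The plan is wrong as written for comparators who entered on a non-COVID-19 vaccine or an outpatient visit. Section 9.2.5.2 lets their recorded post-COMIRNATY time and events count as unexposed, which contradicts the contrast in 8.2 and 9.3.1.2. It would be too strong to say this of all comparators.

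The direction, toward 1, assumes that crossover is unrelated to outcome risk apart from any vaccine effect. The size cannot be fixed from the protocol. A fall from 3 to 2.50 at 10% contaminated person-time applies only if the effect persists through follow-up; a reader should not carry it over to all outcomes. For an effect limited to 42 days, the one-year RR moves only from 1.23 to 1.20 at 10% crossover. That is small in absolute terms, though it still understates harm. The correction belongs in the plan because it removes an avoidable bias from the Phase 2 primary estimate.

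**What to change.** Add to section 9.2.5.2: follow-up of every comparator, whatever the qualifying encounter, ends at first receipt of COMIRNATY 2023-2024, whether or not that person then enters the COMIRNATY cohort. Post-dose time and events can then count only in the COMIRNATY cohort. The sentence should also say that the day of the dose is not comparator time, because Table 2 starts some risk intervals on day 0. The different-brand rule and the SCRI follow-up rules can stay as they are.

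The cost is one sentence, a rerun of the Phase 2 analyses and somewhat shorter comparator follow-up. Censoring may be informative, since the decision to be vaccinated can track health status. A sensitivity analysis, for example with inverse-probability-of-censoring weights, can check this.

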## 9.3. Variables

### 9.3.1. Exposures

#### 9.3.1.1. COMIRNATY 2023-2024 Formula

The SCRI analysis and the cohort analysis will include individuals with exposure to the COMIRNATY 2023-2024 Formula. The code list to define exposure is available in [Annex 2 \(Appendix I\)](#).

### 9.3.1.2. Comparator Cohort

The Phase 2 cohort study will include comparators with no recorded vaccination for the COMIRNATY 2023-2024 Formula. To improve comparability with the COMIRNATY 2023-2024 Formula vaccinated cohort, patients included in the comparator cohort will be required to have a code indicative of a healthcare encounter, including one of the following:

- Presence of a code for a vaccine other than the COMIRNATY 2023-2024 Formula;
- Presence of a code indicative of an outpatient healthcare encounter.

Codes relating to other vaccines or outpatient visits are provided in [Annex 2 \(Appendix II\)](#).

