### **9.2.3. Vaccination Date and Cohort Entry Date**

In the Phase 1 SCRI analysis, the date of first vaccination with the COMIRNATY 2023-2024 Formula will be set as the vaccination date. For the analysis assessing individuals who receive more than one dose of the COMIRNATY 2023-2024 Formula, each vaccination with the COMIRNATY 2023-2024 Formula will be set as a new vaccination date.

In the Phase 2 cohort analysis, the cohort entry date will be the date individuals in the COMIRNATY group receive their first recorded dose of the COMIRNATY 2023-2024 Formula. For individuals in the comparator cohort, the cohort entry date will be set as the date of first qualifying healthcare encounter. Propensity score-matched comparators will also be matched on age group and calendar time. Regarding age, matching will be performed between patients within age groups (e.g., 6 months–4 years, 5–11 years, 12–17 years, 18–64 years, and  $\geq 65$  years). Regarding calendar time, patients will be matched within 14-day windows (e.g., 01 September 2023 to 14 September 2023, 15 September 2023 to 28 September 2023) in which individuals in the exposed cohort will have received vaccination with the COMIRNATY 2023-2024 Formula and individuals in the unexposed cohort will have had a healthcare encounter but no recorded vaccination with the COMIRNATY 2023-2024 Formula. Alternate calendar periods (e.g., one month) may be empirically explored.

For matched comparators, the cohort entry date will be the date within the matched 14-day calendar period on which they had a healthcare encounter.

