### 9.3.3. Covariates

All members of the study cohorts will be described according to covariates identified in the claims data. Demographic attributes will be determined on the vaccination/cohort entry date, while other factors will be assessed in the one year prior to the cohort entry date. Unless specified as for descriptive purposes only, the covariates listed will be included in the PS models. All variables are binary unless otherwise specified.

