### **COVID-19 Vaccination – Descriptive only (not for inclusion in PS model)**

- Site of vaccination (e.g., outpatient, pharmacy)
- Source of vaccination information (e.g., CPT code, NDC)
- Number of doses prior to 2023-2024, by vaccine product
- Average number of days between doses of COMIRNATY 2023-2024 Formula, among those with multiple doses

Code lists for covariates are included in [Appendix IV](#).

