### 17.2.3. Outpatient Codes

**CPT Codes**

99201-99205      Outpatient physician evaluation and management  
99211-99215  
99241-99245  
99354-99355  
99381-99387  
99391-99397

---

 CPT copyright 2024 American Medical Association. All rights reserved.

 CPT copyright 2024 American Medical Association. All rights reserved.

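### Phase 2 comparators may enter on a problem-driven office visit while recipients enter on a vaccination, so outcome ascertainment around Day 0 is unequal in the pooled primary analysis

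*Protocol*

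**What the plan says.** Protocol 9.3.1.2 gives comparators two routes of entry: "Presence of a code for a vaccine other than the COMIRNATY 2023-2024 Formula" or "Presence of a code indicative of an outpatient healthcare encounter". The stated aim of requiring an encounter is "To improve comparability with the COMIRNATY 2023-2024 Formula vaccinated cohort".

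Section 17.2.3 defines the second route under the label "Outpatient physician evaluation and management". It lists 99201-99205, 99211-99215, 99241-99245 and 99354-99355 (office visits, consultations, prolonged services) together with the preventive-visit codes 99381-99387 and 99391-99397. Nothing limits the reason for the visit.

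Under 9.2.3, for comparators "the cohort entry date will be set as the date of first qualifying healthcare encounter". For recipients it is "the date individuals in the COMIRNATY group receive their first recorded dose" of the 2023-2024 Formula. Section 9.3.3 names pharmacy as one possible vaccination site and keeps site out of the propensity score (PS).

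On covariates, 9.3.3 says that demographics are taken at entry and "other factors will be assessed in the one year prior to the cohort entry date". The PS model in 9.7.2.1 holds prior-year visit counts, comorbidities and medications, but no term for why the entry visit took place. The standardized differences cover only covariates in that model.

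Section 17.3 defines an outcome by a single diagnosis code unless stated otherwise, and defines outpatient outcome visits by the same 17.2.3 list. The primary analysis (9.7.2.2, 9.7.2.3) pools all matched comparators. Secondary analyses split them into other 2023-2024 COVID-19 vaccine, non-COVID-19 vaccine, and visit without vaccine.

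**The concern.** The two arms are sampled on different kinds of day. A recipient is sampled on a preventive act. A comparator may be sampled on a day when symptoms brought them to a clinician, with tests and referrals to follow. A diagnosis coded at the next work-up visit falls on Day 1 or later and counts as an incident comparator event. Section 9.9 accepts that rule-out codes occur in claims but does not connect this to comparator entry.

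The planned adjustment cannot see the difference. Two people with the same prior-year history can match closely and pass the balance check when one enters with new symptoms and the other at a pharmacy counter.

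Phase 2 is a comparison of harms, and 9.9 makes the cohort the primary analysis for chronic outcomes such as multiple sclerosis. A rate ratio biased downward would understate harm and make the record-review threshold of 3.0 in 9.3.2 slightly harder to reach.

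**Working it through.** The protocol gives no visit mix and no bias figure, so there is nothing to reproduce. The check has three parts.

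**1. Which outcomes are exposed (Table 2)**

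- Outpatient claims count for 11 of 20 outcomes: Bell's palsy, cerebral venous sinus thrombosis, seizures, glomerulonephritis, herpes zoster, immune-mediated myositis, immune thrombocytopenia, Kawasaki disease, multiple sclerosis, myocarditis/pericarditis and pulmonary embolism.
- Six are inpatient only, and three are inpatient or emergency department.
- The clean period includes Day 0 for 20 − 3 = 17 outcomes. The exceptions are ADEM, anaphylaxis and seizures.

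**2. Two opposing mechanisms**

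- Work-up after entry: extra comparator events from Day 1 lower the rate ratio.
- Day 0 exclusion, for the 17 outcomes: an office-visit comparator whose condition is coded at entry is removed. A pharmacy-vaccinated recipient with the same condition has no entry diagnosis, stays in, and becomes an event at the next coded visit. This raises the rate ratio.

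**Seizures.** The clean period runs from Day −42 to Day −1, follow-up starts on Day 0, and outpatient claims count. The code list in 17.3 includes ordinary epilepsy diagnoses such as G40.909. A comparator who enters on an epilepsy visit, with no such code in the prior 42 days, is an event on Day 0 through the entry visit itself. A recipient vaccinated at a pharmacy has no equivalent claim. This follows from the definitions and needs no assumed rate.

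**3. Illustrative size of the first mechanism alone**

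Assumed, because the documents give neither: s, the share of all comparators entering on a problem visit, and k, their outcome-rate multiplier for the first 42 days. From the protocol: follow-up of up to 365 days. Forty-two days is the longest risk interval in Table 2, borrowed here as the length of the raised-rate period. With a true rate ratio of 1, a rare outcome and complete follow-up:

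observed RR = 1 / (1 + s × (k − 1) × 42/365)

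For example, s = 0.5 and k = 3 give 1 / (1 + 0.5 × 2 × 0.1151) = 1 / 1.1151 = 0.90.

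| s | k = 1.5 | k = 2 | k = 3 |
|---|---|---|---|
| 30% | 0.98 | 0.97 | 0.94 |
| 50% | 0.97 | 0.95 | 0.90 |
| 70% | 0.96 | 0.93 | 0.86 |

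Over the same range, the true ratio needed to read 3.0 runs from 3 × 1.0173 = 3.05 to 3 × 1.1611 = 3.48.

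**The case against.** The strongest reply is that the plan already has the informative comparisons. The secondary analyses against recipients of another 2023-2024 COVID-19 vaccine and of a non-COVID-19 vaccine use vaccination-day entry, close to how the exposed arm enters. This stands in part: they could reveal the problem. They do not correct the pooled primary estimate, and no planned analysis separates preventive from problem visits.

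Four stronger readings are tempting, and the documents do not support them.

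- A reader might infer that recipients have no clinician contact at entry. None is required, but exposure is also captured from medical claims and outpatient is a named site, so some will be vaccinated at an office visit.
- A reader might infer that the bias must favour the vaccine. The Day 0 exclusion acts in the opposite direction and is absent from the formula above.
- A reader might apply the same formula to the first 42 days alone, where it gives 0.50 for s = 50% and k = 3. The protocol states no 42-day cohort estimate. Phase 2 follows people for up to one year and uses Table 2 for the start of follow-up and the clean periods.
- A reader might extend the point to every result. Nine outcomes count no outpatient diagnoses, and the self-controlled analysis has no comparator cohort and is untouched.

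Prior-year utilization and comorbidity in the PS, and the vaccine and preventive entrants in the comparator pool, also dilute the effect. For seizures, a recipient with epilepsy may be coded at a later visit within the year, which narrows the gap in counts but does not make the entry visit a valid event. Finally, preventive-visit attendees may be healthier than recipients, so restricting entry has its own risk of bias. That is a reason to report both comparators.

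**Conclusion.** The point holds as a recommended improvement. Entry rules differ between the arms in a way that affects when diagnoses are coded, the planned adjustment does not address it, and the limitations section does not mention it. The direction is probably toward the vaccine looking safer.

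Under the assumed inputs, the work-up mechanism moves a true ratio of 1 to about 0.98 to 0.86 over one year. That is small to moderate, and it rests on s, k and the 42-day duration, none of which the documents supply. Early censoring would weaken the dilution, and the Day 0 exclusion would offset some of the effect. The concern applies mainly to the 11 outcomes that count outpatient claims. The seizure case is a definitional fault and stands without these assumptions.

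**What to change.** - In 9.3.1.2 and 17.2.3, restrict outpatient-visit entry for the primary comparator to 99381-99387 and 99391-99397, alongside the vaccine encounters. The other visit codes stay valid for identifying outcomes.
- Refit the PS, re-match, and report the comparator using all listed visit codes as a sensitivity analysis.
- If the primary comparator cannot be changed, pre-specify the restricted-entry comparator as a sensitivity analysis for every outcome.
- For non-febrile seizures, do not count a diagnosis on the comparator's own entry-visit claim as an outcome. This is needed under either entry rule, since a preventive visit can also carry an epilepsy code.
- State the unequal entry, and the uncertain direction of its effect, in 9.9.

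The cost is more than a code filter. Changing the entry codes moves Day 0 for some comparators, so baseline, PS and matching must be redone. There will be fewer comparators and possibly some unmatched recipients in older or sicker strata. Matching at up to 1:10 is contemplated in 9.7.2.1, so the sponsor can check whether the smaller pool suffices. Version 3.0 is dated 18 March 2026 and the final report is planned for 30 April 2026, so the sensitivity-analysis route may be the practical one.
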